## **7.0 STUDY PROCEDURES**

### **7.1 Screening Visit**

Once patients have been identified and have expressed interest in learning more about this possible study opportunity, staff will receive permission to screen these patients using the inclusion and exclusion criteria. Permission for screening will be obtained using an oral screening consent form (see SOP for Screening, Consent, Locator, Initiation, Assessment and Blinding). Those who screen positive will then be provided with the full consent documents for study enrollment.

#### **7.1.1 Informed Consent Procedures for Participants**

Study procedures and the potential risks and benefits of participating in the trial will be explained to participants (see SOP for Screening, Consent, Locator, Initiation, Assessment and Blinding). We also will obtain permission to audio record intervention sessions for intervention fidelity monitoring purposes. Given the multi-site nature of the trial, it is possible that ancillary studies will be proposed before or after the study begins recruitment. For this reason, during the informed consent process, we also will seek permission to contact the participant in the future about other study opportunities. Staff will be available to answer questions about the consent form while participants are reviewing it. Prior to signing the consent form, the participant must pass a brief consent comprehension tool to illustrate comprehension of the study activities. After successful completion of the tool and signing the consent form, participants will be given a copy to keep for their records. The informed consent process will take approximately 20 minutes to complete.

Participants who pass the screen and consent will complete a locator information form which will be used to contact them to remind them of follow-up visits and to locate participants who cannot be found. Trained study staff members will work with the participant to complete this form. When completing this form, participants will be required to provide their names, addresses, and telephone numbers as well as contact information for at least 2 other persons. Locator information will be updated at the follow-up visits and at any other time during the study, as needed. The locator information form will take approximately 5-10 minutes to complete. Patients not able to provide at least 2 collateral contacts will not be allowed to participate in the study. Participants will be directed to inform their 2 collateral contacts that they are in the study. The participant will also be informed that she may disclose any level of detail about her involvement with the study to her locator contact she wishes. By sharing this information, should the study contact the collateral, these individuals will know the participant is already in the study. Locator information will be reverified at each follow up visit.

### **7.2 HIPAA Authorization and Medical Record Release Forms**

As part of the enrollment process, we will obtain written permission from the patient to access their University of Utah and University of Pittsburgh medical records. We will likewise obtain permission from participants to access services records from community agencies where they may obtain health and social services.

### **7.3 Baseline Visit**

After patients complete the locator information form, they will complete a baseline assessment. The study staff member administering the assessment will have completed all required CITI training modules. Drs. Cochran and [name] will also train the study staff in survey administration methods, specifically with how to appropriately ask sensitive questions and to respond to responses from patients regarding sensitive topics (including reporting information to study PIs

by the participant regarding intention to harm self or others). Training will include Drs. Cochran and [name] going over the survey with the research assistant, modeling appropriate administration, practicing administration, and supervised administration for the first 3 subjects enrolled in the study. The study baseline assessment will happen at the SUPeRAD clinic, research offices, Magee Womens Research Institute, or other appropriate and private locations. Assessments will be completed using REDCap surveying technology. Survey responses will be reviewed by study staff to ensure completeness. Completed surveys will be immediately saved online. The baseline assessment will take approximately 30-45 minutes.

#### 7.4 Randomization

Following the baseline assessment, participants will be randomized on a 1:1 basis to PN or standard care (i.e., short-term case management + referral). The study statistician will create a randomization list to assign patients to treatment or control conditions. The statistician will also review the randomization data on a regular basis to ensure that the scheme is being implemented according to plan. If a participant drops out of the study at any point after randomization, the randomization slot will not be re-allocated to a new patient due to the intent-to-treat nature of the study.

#### 7.5 Treatment/Intervention

**Standard care.** The standard care condition at Magee and the University of Utah hospitals includes brief case management and referral. The brief case management involves the participant speaking to a hospital social worker who conducts a patient needs assessment in the areas of behavioral health and social services. All patients will be referred to MAT and any identified behavioral health or social service needs. For MAT, Magee-Womens Hospital offers resources for onsite induction to methadone or buprenorphine (mono-product), with continued methadone maintenance only provided by community partners and continued buprenorphine offered by an internal Magee clinic or community partners. University of Utah patients are offered buprenorphine induction and maintenance (buprenorphine-naloxone product) at a local University of Utah outpatient clinic or from community partners. Methadone services for University of Utah patients are only provided by community partners. Staff social workers at Magee and the University of Utah will be provided with information on the study each quarter during the study recruitment phase and be instructed to closely follow and not deviate from their hospital standard care protocol. These quarterly meetings/trainings will be delivered in order to prevent threats to internal validity and biasing study outcomes.

**Patient navigation (PN).** Details of the navigation can be found in the PN Intervention Manual. The PN intervention will be delivered by the study navigator. Table 4 contains details of the PN intervention. The PN intervention will initiate following participant recruitment. *It is important to note that in Table 2, PN sessions do not strictly coincide with specific weeks of pregnancy since the women can be recruited up to ≤32 weeks of gestation.* The prenatal portion of the intervention includes up to 10 sessions delivered prior to delivery. The postnatal portion of the intervention will be delivered as 4 sessions over 8 weeks. Women who complete the intervention before delivery will receive regular calls/texts until delivery wherein the navigator will encourage and reinforce abstinence and treatment retention (see SOP for continued engagement). All contact will be reported by staff in a participant contact log developed for the study that will be used to quantify level of patient contact.

Our PN model is based on the work of Parker and the recently completed Project HOPE study (Hospital Visit as Opportunity for Prevention and Engagement for HIV-Infected Drug Users). The study navigators will receive a two day training in motivational interviewing tailored to the study intervention manual and must demonstrate motivational interviewing proficiency assessed by trainers. The navigators will also receive a one-day training in the intervention protocol by study

investigators. Navigators will complete 3-5 practice sessions, which will be audio recorded and assessed using intervention checklists. Feedback from practice sessions will be shared with navigators in directly and in group discussions. Intervention fidelity checking will also occur throughout the study with navigators audio recording all PN sessions, which will be selected at random for fidelity assessments and feedback by the study coordinator and project investigators.

The primary goal of the current PN intervention is linking patients before and after delivery to treatment/psychosocial care and clinical support for participants' retention in those services. All PN patients will be referred to MAT by the study navigator (see standard care description above for site differences for MAT resources). *It is through the navigator linking and helping to retain participants to OUD, other SUD, medical, mental health, social, and family services that will stimulate positive short- and long-term outcomes for mother and infant.* While Magee and the University of Utah hospitals facilitate initiation into MAT, a major challenge for women is linking to services for ongoing MAT and subsequently being retained in care. Patients will be encouraged to work with their providers to choose the form of medication, buprenorphine or methadone, which will best meet their needs. The navigator will support and encourage the patient to follow through with this treatment. The PN intervention will also target better compliance with pre/postnatal maternal healthcare, more effective transition of newborns into pediatric care, and relapse prevention (i.e., Aim 2). The PN intervention specifically encompasses two complementary and necessary services: strengths-based case management (SBCM) and 1-to-1 clinical support (see Table 2). PN sessions will last 1-1.5 hours. Furthermore, given the challenges keeping this population engaged in care, the intervention emphasizes community outreach. For example, the navigator can visit the neighborhoods to meet participants' social and family networks to empathically encourage and support engagement with health, social services systems, and recovery support (i.e., narcotics anonymous, alcoholics anonymous) if patients become disengaged in care or follow up.

*SBCM* is an evidenced-based component of the PN model that has been demonstrated to help individuals with substance use disorders and chronic health conditions engage in needed care. The navigator will apply the specialized skills of SBCM to link patients to ongoing MAT services and guide participants to active engagement in health and social services. SBCM gives patients responsibility for, and ownership of, their recovery. SBCM has been shown to have a variety of positive effects, particularly treatment retention and linkage with community services. SBCM utilizes patients' strengths for goal setting and developing a working alliance between providers and patients. The specific elements the navigator will focus on include: helping patients obtain and complete paperwork; accessing and engaging in drug/mental health counseling/treatment/mutual support, social services uptake, MAT linkage/retention, and engagement in pre/post-natal care and pediatric/developmental care for newborns. It is important to note that participants and the navigator will collaborate to identify *already existing health and community services* that participants will subsequently engage in with the navigator's assistance.

*One-to-one clinical support* is a paramount PN component for identifying, establishing, and retaining health behavior improvement goals. One-to-one clinical support is designed to motivate and assist patients recognize and overcome internal/external barriers to care, including: emotional support, decision support, lifestyle change support, monitoring outcomes of screening/diagnostics, health behavior, and HIV/HCV prevention education. HIV/HCV prevention messaging will address needle sharing and unsafe sex. Patients will receive support and verbal reinforcement for completion of paperwork, engaging in drug/mental health treatment, social services uptake, agonist adherence, and engaging in pediatric/developmental care for their infants. One-to-one clinical support will be delivered using *motivational interviewing skills*. Motivational interviewing is an evidence-based approach for promoting health behavior change in healthcare settings. The navigator will collaborate with participants to resolve ambivalence toward change by guiding them to establish their own goals

and strategies, giving them ownership in outcomes, helping build self-efficacy, and increasing the likelihood of achieving abstinence and MAT retention goals. We have also aligned PN session objectives to support and assist women to prepare for, discuss, and successfully complete specific maternal milestones.

## **7.6 Premature Withdrawal of Participants**

All participants will be followed for the duration of the study unless they withdraw consent, are no longer pregnant due to spontaneous abortion (miscarriage) or termination that was unplanned at the time of enrollment, die, or the investigator or sponsor decides to discontinue their enrollment for any reason. Reasons for the investigator or sponsor terminating a participant from the study may include, but are not limited to, the participant becoming a threat to self or others, lack of funding, DSMB early termination of the study for safety or effectiveness determination.

## **7.7 Study Halting Rules**

The study will be halted based on lack of funding.

## **7.8 Follow-Up**

Participants will be assessed at baseline, following the completion of the prenatal portion of the intervention, following the postnatal portion of the intervention at approximately 2 months post delivery, and 6 months following delivery. See SOP for data collection. Appointments for follow up sessions will be made with participants by study staff. At the follow up visits, the first step in the assessment will be to confirm participant contact information and to ensure locator information has not changed. Following contact information verification, patients complete a survey assessment similar that completed at the baseline assessment. The study follow up assessments will happen at the SUPeRAD clinic, research offices, Magee Womens Research Institute, or other appropriate and private locations using REDCap surveying technology. Survey responses will be reviewed by study staff to ensure completeness. Completed surveys will be immediately saved online. The follow up assessments assessment will take approximately 30-45 minutes at each visit—see urine drug screen SOP.

## **7.9 Blinding**

### **7.9.1 Type of Blinding**

This study is a single blinded randomized clinical trial.

### **7.9.2 Maintenance of the Blind**

The individuals blinded to the study condition will be those conducting the study assessments. The baseline assessment will be blinded given that the randomization will not be revealed until after the assessment is completed. The follow up assessments will be conducted by a blinded research assistant.

### **7.9.3 Breaking the Blind**

As the research assistant is the only blinded party, there is no scenario in which the blind will need to be broken. Investigators providing clinical management and decision-making are informed of each participants randomization result.

## **7.10 Participant Reimbursement**

Women will receive \$30 for enrolling in the study and completing the baseline assessment, \$40 for completion of the second assessment, \$50 for the third assessment, and \$75 for the final assessment. Patients that complete all 4 assessments will be given a completion bonus of \$50. Patients will also be provided with a \$10 compensation for each navigator session they attend to cover costs associated with transportation and/or parking. Participant compensation administration will be carried out by the study project coordinator or research assistants.

## 8.0 STUDY ASSESSMENTS

*A full and complete list of all assessments used in the study is to be included in the following sections.*

Outcome	Domain	Name	Source	Screen	Base	PreNat	2mo	6mo
1/2ary	Engage	Treatment Services Review	Self-Report		x	x	x	x
1/2ary	SUD	Timeline Follow Back	Self-Report		x	x	x	x
1ary	Engage	Substance use treatment visits	Medical record		x	x	x	x
1ary	Engage	Psychiatric care visits	Medical record		x	x	x	x
1ary	SUD	Urine toxicology	NA	x	x	x	x	x
1ary	Engage	Social service visits	Agency record		x	x	x	x
2ary	HIV/HCV risk	Risk Behavior Assessment	Self-Report		x	x	x	x
2ary	Social	Maternal Social Support Index	Self-Report		x	x	x	x
2ary	Social	Parenting Stress Index-Short Form	Self-Report		x	x	x	x
2ary	Social	Maternal Attachment Inventory	Self-Report		x	x	x	x
2ary	Engage	Adequacy of Prenatal Care Utilization	Medical record				x	
2ary	Engage	Pre/post maternal care visits	Medical record		x	x	x	x
2ary	Engage	Pediatric visits	Medical record		x	x	x	x
2ary	SUD	Neonatal abstinence syndrome	Medical record				x	
2ary	Engage	Pre/post maternal care visits	Medical record		x	x	x	x
2ary	Engage	Pediatric visits	Medical record				x	x
Covar	SUD	Drug Abuse Severity Test 10	Self-Report		x	x	x	x
Covar	SUD	Alcohol Use Disorder	Self-Report		x	x	x	x

		Identification Test						
Covar	SUD	Fagerstrom Test for Nicotine Dependence	Self-Report		x	x	x	x
Covar	Health	Short Form 36	Self-Report		x	x	x	x
Covar	Psych	Patient Health Questionnaire	Self-Report		x	x	x	x
Covar	Social	Addiction Severity Index (employment)	Self-Report		x	x	x	x
Covar	SUD	DSM 5 Checklist	Self-Report	x	x	x	x	x

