## **4.0 OUTCOME MEASURES**

### **4.1 Primary Outcome Measure**

The primary outcomes in this study are (1) OUD and other SUD treatment linkage/retention, (2) opioid abstinence, (3) adherence to MAT, and (4) linkage/retention in psychosocial services.

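### The primary count of substance use treatment visits comes from the universities' medical records, although methadone and some buprenorphine care is given by community partners

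*Combined protocol and SAP*

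**What the plan says.** Section 4.1 puts this first among four primary outcomes: "1) OUD and other SUD treatment linkage/retention". The section 8.0 table lists "Substance use treatment visits" as a primary measure in the engagement domain, at baseline, end of the prenatal portion, 2 months and 6 months, with the medical record as source. In the same table "Social service visits", also primary, has the agency record as source. The "Treatment Services Review" is a self-report engagement measure at the same four times, marked as serving both primary and secondary outcomes.

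Section 7.2 seeks access to the medical records of the two universities. It adds that the study will obtain "permission from participants to access services records from community agencies where they may obtain health and social services".

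Section 7.5 describes where treatment takes place. Magee can start either medication on site, "continued methadone maintenance only provided by community partners and continued buprenorphine offered by an internal Magee clinic or community partners" being the arrangement afterwards. At Utah, buprenorphine is available from a university outpatient clinic or from community partners, and "Methadone services for University of Utah patients are only provided by community partners".

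**The concern.** The table separates hospital records from agency records and assigns only the former to substance use treatment visits. Yet much of the treatment that the trial tries to sustain happens outside the hospitals. Section 7.5 itself says that the hospitals help women start medication-assisted treatment (MAT) and that the hard part is linking them to ongoing treatment and keeping them there. For methadone, that later phase lies wholly with community partners.

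A Magee patient who starts methadone on site and continues with a community partner could look like a dropout in the university record. A Utah patient on methadone might never appear as treated. Section 10.2.2 also notes that more outside agencies in Pennsylvania are offering services to women with substance use disorders.

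At stake is the estimated effect on the first primary outcome, which this pilot is meant to carry into planning a fully powered trial.

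**Working it through.** **The plan's own figures.** Section 10.2.2 bases the sample size on feasibility: (141 + 58) potential recruits per year × 15/12 years × 0.70 × 0.70 = 121.9, which reproduces the stated 122 (61 per arm). No linkage rate enters this product, so the choice of data source does not change the sample size. The section also states the precision expected for odds ratios. With 61 per arm, 95% factor = exp(1.96 × √[1/(61·p₁(1−p₁)) + 1/(61·p₀(1−p₀))]), ignoring site clustering. Over most control rates from 0.1 to 0.8 and odds ratios from 1 to 3 this gives upper factors of about 2.0 to 2.8, which broadly agrees with the stated 2 to 3.

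**Assumed inputs.** The documents give neither linkage rates nor the share of treatment recorded outside the universities. For illustration, take true linkage of 0.70 with PN and 0.50 with standard care. Then OR = (0.70/0.30)/(0.50/0.50) = 2.33, and the risk ratio is 0.70/0.50 = 1.40.

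**Method.** Observed rate = true rate × capture fraction, with no false positives. Power at 61 per arm, two-sided 0.05, is Φ[(difference − 1.96·SE₀)/SE₁], where SE₀ is pooled and SE₁ unpooled.

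**Equal capture in both arms**

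| Off record | Observed PN v standard care | Difference | Risk ratio | OR | Power |
|---|---|---|---|---|---|
| 0% | 0.70 v 0.50 | 0.20 | 1.40 | 2.33 | 0.62 |
| 10% | 0.63 v 0.45 | 0.18 | 1.40 | 2.08 | 0.51 |
| 30% | 0.49 v 0.35 | 0.14 | 1.40 | 1.78 | 0.35 |
| 50% | 0.35 v 0.25 | 0.10 | 1.40 | 1.62 | 0.22 |

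For example, at 30%: (0.49/0.51)/(0.35/0.65) = 1.78. The risk ratio is unaffected, but section 10.2.2 plans odds ratios and section 10.3 plans χ² tests and a logistic mixed model. The odds ratio and the difference both shrink.

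**Unequal capture**

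| Capture PN / standard care | Observed | OR |
|---|---|---|
| 70% / 80% | 0.49 v 0.40 | 1.44 |
| 50% / 70% | 0.35 v 0.35 | 1.00 |
| 70% / 60% | 0.49 v 0.30 | 2.24 |
| 80% / 60% | 0.56 v 0.30 | 2.97 |

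The last row exceeds the true 2.33, so the bias can go either way.

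**The case against.** The primary outcome does not rest on this row alone. The Treatment Services Review also measures engagement at every assessment, and nothing in the table confines it to hospital care. Section 7.2 plans access to community agency records that cover health as well as social services. The data collection SOP cited in sections 3.2 and 7.8 is not part of these documents and may join the sources. Section 10.2.2 also says that definitive estimation and testing are not the aim of this pilot.

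Much of this stands. It means that under-counting is a risk of following the table, not an established fact. It does not close the gap, because no text sends agency records to this row or says how records and self-report combine. Self-report is also a weak substitute: section 7.9 blinds only the assessors, and section 7.5 has navigators verbally reinforce treatment engagement.

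A reader might infer three stronger things, none of which the documents support:

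- **Greater loss in the PN arm.** Navigators do work with existing community services, but also with health services, and both arms are referred to MAT with the same site resources. No capture rates by arm are given.
- **Every woman on community methadone counts as not linked.** On-site induction at Magee may already register linkage, and no linkage threshold is stated.
- **The same fault for psychiatric care visits.** That row also uses the medical record, but section 7.5 places only MAT, not psychiatric care, with community partners.

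**Conclusion.** The point holds for the substance use treatment visits row. The source stated in section 8.0 is incomplete when set against the care pathway in section 7.5. The exposure is mainly to retention at both sites and to methadone linkage at Utah.

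Its size cannot be computed from the documents. Under the assumed 70% v 50%, losing 30% to 50% of linkages equally in both arms would move the odds ratio from 2.33 to between 1.78 and 1.62. If capture differs by arm, neither the size nor the direction of the bias is known. This should be corrected, because a pilot looking for a signal of benefit needs a reasonably complete count and the remedy is already within the plan's reach.

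**What to change.** In the section 8.0 table, change the source for substance use treatment visits to medical record plus community agency record, using the permissions planned in section 7.2. Then state that:

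- a visit found in either source counts;
- agency records are requested by the same procedure in both arms, for example from each site's known community MAT partners and from any agency the participant names;
- the Treatment Services Review is a supplementary source, with its role written down in advance;
- agency records that could not be obtained are reported by arm and site.

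The cost is some coordinator time for record requests. The sample size does not change, and agency records are already to be collected for social service visits.

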## **3.0 STUDY DESIGN**

### **3.1 Overview of Study Design**

Opioid dependent pregnant women who present at Magee-Womens Hospital of UPMC and the University of Utah Hospital ≤32 weeks of gestation will be approached for potential participation in our OPTI-Mom 2.0 study. Our prenatal intervention is designed to span between 8 and 14 weeks and is dependent on gestational age at the time of enrollment. This allows study participants to receive the maximum amount of intervention sessions available prior to delivery. The following Approach Section describes preliminary data we have collected to support this proposal, project design, inclusion/exclusion criteria for participation, recruitment, intervention conditions, data collection/analysis, and timeline.

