### **3.2 Duration of Study and Visit Schedule**

This study will require 36 months to complete. Patient recruitment will last 15 months, intervention delivery will last 24 months, and assessments will last 30 months. As indicated, the prenatal portion of the study will include up to 10 sessions that span between 8 and 14 weeks. In addition, we will also provide 4 postnatal interventions that span 8 weeks. Each of these sessions lasts 1-1.5 hours. All participants, in the treatment or control group, will be required to complete 4 standardized assessments, which will occur at baseline, following the completion of the prenatal portion of the intervention, following the postnatal portion of the intervention at approximately 2 months post delivery, and 6 months following delivery. See SOP for data collection.

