### **5.1 Participant Inclusion Criteria**

This study will recruit women for participation meeting the following inclusion criteria:

- Adult ( $\geq 18$  years)
- English speaking
- Pregnant women (pregnancy status verified by gestational age  $>6$  weeks from last menstrual period confirmed by ultrasound)
- OUD verified by examination of medical records for an OUD diagnosis and the DSM Checklist (modified from the DSM-IV to confirm current diagnosis for substance use disorders)
- Plan to carry their babies to delivery verified by patient self report

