### **5.2 Participant Exclusion Criteria**

All women meeting any of the exclusion criteria at baseline will be excluded from study participation:

- Experienced a psychotic or a manic episode in the last 30 days documented in their medical record or self report
- Beyond the 32nd week of gestation
- Cannot provide collateral contact information of 2 persons
- Cannot provide a reliable phone number
- Plan to move from the area within study recruitment to 6 months after their delivery
- Inability or unwillingness of subject to give written informed consent.
- Other factors that would cause harm or increased risk to the participant or close contacts, or preclude the participant's full adherence with or completion of the study
- Has been on buprenorphine or methadone for  $>6$  weeks.

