#### 10.1.1 Study Hypotheses

H1: PN recipients will have superior linkage and retention in: (a) OUD and other SUD treatment, (b) psychosocial services, and (c) pre/postnatal care compared to standard care.

H2: A larger portion of PN patients will be (a) MAT adherent and (b) drug abstinent compared to standard care.

H3: Higher levels of engagement/retention in care will positively moderate improvements in: (a) abstinence, (b) HIV/HCV risk behaviors, (c) depression/anxiety, and (d) child/mother outcomes (e.g., health care, NAS, stress).

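### The prenatal care adequacy index is scored once after delivery with no baseline although women enter up to 32 weeks, so an unadjusted comparison would attenuate any PN effect on it, and the plan does not say which measure tests H1(c)

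*Combined protocol and SAP*

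**What the plan says.** Section 8.0 has two maternal measures that bear on prenatal care, both secondary and both from the medical record.

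- "Adequacy of Prenatal Care Utilization" is marked at one visit only, 2 months after delivery.
- "Pre/post maternal care visits" is marked at baseline, at the end of the prenatal intervention, at 2 months and at 6 months. The row appears twice.

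The third part of H1 in section 10.1.1 reads "c) pre/postnatal care compared to standard care", under the claim of superior linkage and retention. No section says which measure tests it, how the index is scored, or what period the index covers.

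On entry, section 5.1 requires a gestational age above 6 "weeks from last menstrual period confirmed by ultrasound". Section 3.1 says women presenting at "≤32 weeks of gestation will be approached for potential participation", and section 5.2 excludes those "Beyond the 32 nd week of gestation". The prenatal intervention has "up to 10 sessions that span between 8 and 14 weeks" (section 3.2). Randomization follows the baseline assessment (7.4) and is stratified by site only (10.1).

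Section 10.3 plans t-tests and chi-square tests by group at each time point, then multilevel growth models with time-invariant and time-varying predictors. It names neither gestational age at entry nor prenatal care before entry. Section 10.2.2 says the sample size of 122 does not rest on a power estimate.

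**The concern.** An adequacy rating taken after delivery, with no stated window, reads most naturally as a rating of the whole pregnancy. On that reading, care attended or missed before randomization counts in both arms, and PN cannot change it. It adds variance, and the part of the score that PN can move is scaled down by its weight.

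The growth models do not help. A variable measured once has no trajectory, so the only test in section 10.3 that clearly fits the index is the unadjusted group comparison.

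The trial is meant to show preliminary benefit and to supply data for a fully powered successor. If the index were used for the prenatal part of H1(c), a real effect on attendance could look weak or absent, and the attenuated estimate could feed into that trial's planning.

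**Working it through.** **The plan's own figure.** Section 10.2.2: (141 + 58) recruits per year x 15/12 years x 0.70 x 0.70 = 121.9, which reproduces 122, or 61 per arm. The plan gives no figure for the adequacy index, so the rest is illustrative.

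**Share of pregnancy before entry**, s = entry week / 40, assuming delivery at 40 weeks: week 6, 0.15; week 12, 0.30; week 20, 0.50; week 26, 0.65; week 32, 0.80. The planned intervention span of 8 to 14 weeks matches entry at 40 - 8 = 32 to 40 - 14 = 26 weeks. Late entry is therefore contemplated, but so is earlier entry, since section 7.5 provides for women who finish their sessions before delivery.

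**Share of visits before entry.** Visits need not be evenly spaced. Assume 14 visits: every 4 weeks from week 8 to 28, every 2 weeks to 36, then weekly to 40. Then 5/14 = 0.36 are past at week 26 and 8/14 = 0.57 at week 32.

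**Attenuation.** Assumptions, none from the documents: PN raises attendance of expected post-randomization visits by 12 points; SD 25 points before and after; correlation 0.4; two-sided 5%; all women enter at the same week.

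- Post-randomization care only: d = 12/25 = 0.48.
- Whole-pregnancy score: d = 12(1 - s) / sqrt[(25s)^2 + (25(1 - s))^2 + 2s(1 - s)(0.4)(625)].
- Power = Phi(d / sqrt(2/61) - 1.96).

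| Score | s | d | Power |
|---|---|---|---|
| Post-randomization only | - | 0.48 | 76% |
| Entry week 12, even visits | 0.30 | 0.39 | 57% |
| Week 20, even visits | 0.50 | 0.29 | 35% |
| Week 26, even visits | 0.65 | 0.20 | 19% |
| Week 26, 14-visit schedule | 0.36 | 0.36 | 52% |
| Week 32, even visits | 0.80 | 0.11 | 9% |
| Week 32, 14-visit schedule | 0.57 | 0.25 | 27% |

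**Second set of assumptions.** With d = 0.5 on post-entry care, equal SDs and correlation 0 to 0.5, power is 79% on post-entry care alone. It is 71 to 78% when post-entry care carries 85% of the score, 36 to 50% at half, and 9 to 10% at a fifth.

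**Adjustment.** Conditioning on pre-entry care leaves residual SD 25 x sqrt(1 - 0.4^2) = 22.9, so d = 12/22.9 = 0.52 and power is 82%. When all women share one entry week, the adjusted index gives the same value, because its effect and its residual SD both shrink by (1 - s). Under the second set, adjustment gives d = 0.50 to 0.58 and power 79 to 89%.

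**Noisier late measure.** A proportion over few visits varies more. With post-entry SD 30, 35 or 40, post-randomization-only power falls to 60%, 47% or 38%. The index suffers too. With post-entry SD 40 and the 14-visit schedule:

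- Week 26: d = 12(9/14) / sqrt[(25 x 5/14)^2 + (40 x 9/14)^2 + 2(5/14)(9/14)(0.4)(1000)] = 7.71/30.4 = 0.25, power 29%.
- Week 32: d = 5.14/26.3 = 0.20, power 19%.

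Both stay below 38%.

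**The case against.** The strongest reply is that the plan already holds a better measure. Maternal care visits are collected at baseline and each follow-up, can enter the multilevel models, and suit linkage and retention at least as well as an adequacy rating. That stands, and it rules out an inference a reader might draw: that prenatal care is scored by one index alone, or that H1(c) is itself diluted. No section assigns the index to H1(c). What remains is that no section assigns the visit records either, and raw visit counts vary with the weeks left to delivery unless they are scaled.

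A reader might also infer that most of the score is fixed at entry. The documents do not show this. The window is inferred from a name and a single time point, the scoring rule is absent, and 32 weeks is a ceiling with no entry distribution given. The lowest powers need entry at that ceiling and evenly spaced visits.

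Nor is there bias between arms: randomization balances earlier care on average. And the trial cannot be faulted for missing a power target, because it sets none and calls definitive testing outside its aim. These replies limit the weight of the point. They do not supply the missing definitions.

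**Conclusion.** The point holds as a conditional attenuation of one secondary outcome in a pilot, together with a gap in specification. The index has one post-delivery score and no baseline, entry runs from just over 6 to 32 weeks, and the comparison that fits the index is unadjusted. If it covers the whole pregnancy, a PN effect on it is understated.

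Under the first set of assumptions the standardized effect falls from 0.48 to 0.39 at entry week 12, 0.20 to 0.36 at week 26 and 0.11 to 0.25 at week 32. These are ranges to show direction and order of size, not estimates for this trial: effect, SD, correlation, visit schedule and entry weeks are all assumed. The direction is firmer. With a non-negative correlation between earlier and later care, a composite containing fixed earlier care cannot have a larger unadjusted standardized effect than post-randomization care alone.

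**What to change.** In section 10.3, or in a separate analysis plan:

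1. State the scoring rule and time window of the adequacy index.
2. Name the measure for the prenatal part of H1(c): prenatal visits from randomization to delivery, from the existing maternal care visit records, scaled to the time or visits expected in that window.
3. Adjust this measure and the index for gestational age at randomization and for prenatal care before randomization.
4. Report the whole-pregnancy index as supportive.

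The cost is wording, a derived variable, and abstraction of visit dates, which the documents do not confirm are recorded. Expected visits would need a stated schedule. The scaled measure is noisier for late entrants and preterm births, where the window is short. A count model with time at risk as offset may therefore be preferable to a simple ratio, since it gives short windows less weight. Adjusting the index recovers precision fully only when women share an entry week, which is a further reason to make the post-randomization measure the main one.
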